9.4.1 Immunogenicity Endpoints

The primary immunogenicity analysis endpoints include:

- Serotype-specific OPA GMTs at 30 days postvaccination (Day 30) for the 15 serotypes contained in V114
- Proportion of participants with a ≥ 4 -fold rise from prevaccination (Day 1) to 30 days postvaccination (Day 30) for OPA responses for the 2 unique serotypes contained in V114

The secondary immunogenicity analysis endpoints include:

- Serotype 3 OPA GMT at 30 days postvaccination (Day 30)
- Proportion of participants with a ≥ 4 -fold rise from prevaccination (Day 1) to 30 days postvaccination (Day 30) for serotype 3 OPA responses
- Serotype-specific IgG GMCs at 30 days postvaccination (Day 30)

- Serotype-specific GMFRs and proportions of participants with a ≥ 4 -fold rise from prevaccination (Day 1) to 30 days postvaccination (Day 30) for both OPA and IgG responses

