9.5 Analysis Populations

9.5.1 Immunogenicity Analysis Populations

The Per-Protocol (PP) population will serve as the primary population for the analysis of immunogenicity data in this study. The PP population consists of all randomized participants without deviations from the protocol that may substantially affect the results of the immunogenicity endpoint(s). Potential deviations that may result in the exclusion of a participant from the PP population for all immunogenicity analyses include:

- Failure to receive any study vaccine at Visit 1 (Day 1)
- Failure to receive correct clinical material as per randomization schedule at Visit 1 (Day 1) (ie, participants who were cross-treated)
- Receipt of prohibited medication or prohibited vaccine prior to study vaccination

Additional potential deviations that may result in the exclusion of a participant's measurement from a specific time point assessment in the PP population for immunogenicity analyses include:

- Receipt of prohibited medication or prohibited vaccine prior to a blood sample collection
- Collection of blood sample outside of the prespecified window (as described in Section 1.3)

The final determination on protocol deviations, and thereby the composition of the PP population, will be made prior to the final unblinding of the database. Participants will be included in the vaccination group to which they are randomized for the analysis of immunogenicity data using the PP population.

A supportive analysis using the Full Analysis Set (FAS) population will also be performed for the primary immunogenicity endpoints. The FAS population consists of all randomized participants who received at least 1 vaccination and have at least 1 serology result. Participants will be included in the vaccination group to which they are randomized for the analysis of immunogenicity data using the FAS population.

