where GMT_1 is serotype-specific OPA GMT for the V114 group and GMT_2 is serotype-specific OPA GMT for the Prevnar 13TM group. A ratio of 2 corresponds to a 2.0-fold increase of OPA GMT in the V114 group as compared with the Prevnar 13TM group. The same statistical criterion has been previously applied to compare Prevnar 13TM with PNEUMOVAXTM23 for serotype 6A, which was unique to Prevnar 13TM [Jackson, L. A., et al 2013]. Rejecting the null hypotheses (H_0) at the 1-sided $\alpha=0.025$ level corresponds to the lower bound of the 2-sided 95% CI on the GMT ratio (V114/ Prevnar 13TM) being >2.0 and would lead to the conclusion that the OPA GMT to V114 for the unique serotype is superior to that of Prevnar 13TM.

To address the first primary immunogenicity objectives, the serotype-specific OPA GMTs at 30 days postvaccination will be compared between vaccination groups. Comparisons will be made through the estimation of serotype-specific OPA GMT ratios for each of the 15 serotypes in V114. Estimation of the GMT ratios and 95% CI and the hypothesis test (ie, 1-sided p-value) will be conducted using a cLDA method proposed by Liang and Zeger [Liang, K-Y and Zeger, S. L. 2000] utilizing data from both vaccination groups. In this model, the response vector consists of the log-transformed antibody titers at baseline and 30 days postvaccination. The repeated-measures model will include terms for vaccination group,

time, the interaction of time-by-vaccination group (with a restriction of the same baseline mean across groups), age stratum (ie, 50 to 64 years, 65 to 74 years, and ≥ 75 years) at baseline, and age stratum-by-time interaction. This model will allow for different baseline means for each stratum, but restrict the baseline mean within the age stratum levels to be the same for both vaccination groups. An unstructured covariance matrix will be used to model the correlation among repeated measurements. The Kenward-Roger adjustment will be used with restricted (or residual) maximum likelihood to make proper statistical inference. This model allows the inclusion of participants who are missing either the baseline or postbaseline measurements, thereby increasing efficiency.

Primary Endpoints/Hypotheses (H3)

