Rejecting the null hypotheses (H_0) at the 1-sided $\alpha=0.025$ level corresponds to the lower bound of the 2-sided 95% CI on the GMT ratio ($V114/ \text{Prevnar } 13^{\text{TM}}$) being >1.2 and would lead to the conclusion that the serotype 3 OPA GMT in the V114 group is superior to the serotype 3 OPA GMT in the Prevnar 13TM group.

To address the first secondary immunogenicity objective, a cLDA method similar as the one used for the first primary immunogenicity objective (H1 and H2) will be used.

Secondary Endpoints/Hypotheses (H5)

The second secondary objective (proportion of participants with a ≥ 4 -fold rise from prevaccination to 30 days postvaccination for OPA responses for participants administered V114 versus participants administered Prevnar 13TM) will be assessed via the following superiority hypotheses for serotype 3:

$$H_0: p_1 - p_2 \leq 0 \text{ versus}$$

$$H_1: p_1 - p_2 > 0$$

where p_1 is the proportion of participants with a ≥ 4 -fold rise for the V114 group and p_2 is the proportion for the Prevnar 13TM group. A difference of 0 corresponds to no difference in the proportions of participants with a ≥ 4 -fold rise of OPA responses from prevaccination to 30 days postvaccination between V114 and Prevnar 13TM. Rejecting the null hypotheses (H_0) at the 1-sided $\alpha=0.025$ level corresponds to the lower bound of the 2-sided 95% CI on the difference ($V114 - \text{Prevnar } 13^{\text{TM}}$) being >0 and would lead to the conclusion that the proportion of participants with a ≥ 4 -fold rise in serotype 3 OPA responses in the V114 group is superior to that in the Prevnar 13TM group.

To address the second secondary immunogenicity objective, the stratified M&N method used for the second primary immunogenicity objective (H3) will be used.

Other Secondary Endpoints

A similar statistical model as used for the first primary objective will be used to address the secondary objective that evaluates the serotype-specific IgG GMCs at 30 days postvaccination with V114 compared with Prevnar 13TM.

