Descriptive statistics with point estimates and within-group 95% CIs will be provided for all other immunogenicity endpoints. For the continuous endpoints, the point estimates will be calculated by exponentiating the estimates of the mean of the natural log values and the within-group CIs will be derived by exponentiating the bounds of the CIs of the mean of the natural log values based on the t-distribution. For the dichotomous endpoints, the within-group CIs will be calculated based on the exact method proposed by Clopper and Pearson [CLOPPER, C. J. and PEARSON, E. S. 1934].

Reverse Cumulative Distribution Curves for both OPA titers and IgG concentrations at 30 days postvaccination with V114 will be graphically displayed by serotype.

A detailed analysis strategy for immunogenicity endpoints is listed in **Table 4**.

Table 4 Analysis Strategy for Immunogenicity Variables

Endpoint/Variable (Description, Time Point)	Primary vs. Supportive Approach [†]	Statistical Method [‡]	Analysis Population	Missing Data Approach
Primary Endpoint				
OPA GMTs at Day 30	P	cLDA [§] (estimate, 95% CI, p-value)	PP	Model-based
	S		FAS	
Proportions of participants with a ≥ 4 -fold rise from prevaccination to 30 days postvaccination for OPA responses for the 2 unique serotypes in V114	P	Stratified M&N (estimate, 95% CI, p-value)	PP	Missing data will not be imputed
	S		FAS	
Secondary Endpoint				
OPA GMTs at Day 30 for serotype 3	P	cLDA [§] (estimate, 95% CI, p-value)	PP	Model-based
Proportions of participants with a ≥ 4 -fold rise from prevaccination to 30 days postvaccination for serotype 3 OPA responses	P	Stratified M&N (estimate, 95% CI, p-value)	PP	Missing data will not be imputed
IgG GMCs at Day 30	P	cLDA [§] (estimate, 95% CI)	PP	Model-based
GMFRs and proportions of participants with a ≥ 4 -fold rise from baseline to 30 days postvaccination for both OPA and IgG responses	P	Descriptive Statistics (estimate, 95% CI)	PP	Missing data will not be imputed

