9.9 Sample Size and Power Calculations

9.9.1 Sample Size and Power for Immunogenicity Analyses

This study will randomize approximately 600 participants into the V114 group and 600 participants into the Prevnar 13™ group and has >90% power for demonstrating noninferiority to Prevnar 13™ for the 13 shared serotypes and superiority for the 2 unique serotypes for V114 at an overall 1-sided 2.5% alpha-level. Sample size is also driven by country-specific requirements (see Appendix 10.7 for details).

The sample size and power calculations are based on the following assumptions:

- 90% evaluability rate (approximately 540 evaluable participants per treatment group).
- The underlying serotype-specific OPA GMT ratios (V114/Prevnar 13™) for the 15 pneumococcal serotypes are the same as that observed in V114-006, which range from 0.78 to 1.86 across the shared serotypes and >6.0 for the V114 unique serotypes.
- The underlying differences (V114 - Prevnar 13™) between proportions of participants with a ≥ 4 -fold rise from prevaccination (Day 1) to 30 days postvaccination (Day 30) for OPA responses are the same as that observed in V114-006 for the V114 unique serotypes, which are >0.1.
- The variabilities for OPA titers in both the V114 group and Prevnar 13™ group are the same as those observed in V114-006. That is, the standard deviations of the natural log titers for the 15 pneumococcal serotypes range from 1.33 to 2.24 for V114 and range from 1.37 to 2.25 for Prevnar 13™.
- The statistical criteria for noninferiority and superiority require the lower bound of the 2-sided 95% CI of the OPA GMT ratio (V114/ Prevnar 13™) to be greater than 0.50 and 2.0, respectively.
- The statistical criterion for superiority requires the lower bound of the 2-sided 95% CI of the difference (V114 - Prevnar 13™) in the proportion of participants with a ≥ 4 -fold rise in OPA response to be greater than 0.1 for the serotypes unique to V114.

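### Does the serotype 3 ≥4-fold-rise superiority test (H5) need a supportive Full Analysis Set analysis like the one planned for H3?

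*Combined protocol and SAP*

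**What the plan says.** Section 9.5.1 fixes the main population: "The Per-Protocol (PP) population will serve as the primary population for the analysis of immunogenicity data in this study". It then limits the second population: "A supportive analysis using the Full Analysis Set (FAS) population will also be performed for the primary immunogenicity endpoints". The FAS is every randomised participant with at least one vaccination and at least one serology result, analysed as randomised.

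Section 9.4.1 makes the ≥4-fold-rise proportion a primary endpoint only "for OPA responses for the 2 unique serotypes contained in V114" (H3). The serotype 3 proportion (H5) is listed as secondary.

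Table 4 in Section 9.6.1 follows this split. The H3 row has a primary line (PP) and a supportive line (FAS). The row for the "rise from prevaccination to 30 days postvaccination for serotype 3 OPA responses" has the PP line alone, with the entry "Missing data will not be imputed".

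On method, Section 9.6.1 says: "To address the second secondary immunogenicity objective, the stratified M&N method used for the second primary immunogenicity objective (H3) will be used". H5 is tested at 1-sided 0.025 and succeeds if the lower 95% bound of the difference exceeds 0.

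For titers, serotype 3 is part of the primary endpoint: "Comparisons will be made through the estimation of serotype-specific OPA GMT ratios for each of the 15 serotypes in V114". That model has a supportive FAS line in Table 4.

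**The concern.** H5 is more than a descriptive secondary. It has its own null and alternative, a p-value in Table 4 and a stated superiority conclusion. The amendment that added it gives as its reason the limited effect of the comparator on serotype 3 disease in adults, so readers will look closely at a positive result.

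H5 is also more exposed to PP exclusions than the titer comparison. It needs both a Day 1 and a Day 30 titer. An out-of-window draw, or a prohibited medication or vaccine before a draw, may remove one of the two and with it the participant. The constrained longitudinal model used for titers keeps a participant who has only one measurement.

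H1, H2 and H3 all have an FAS analysis. H4 has one in substance, because serotype 3 is among the 15 serotypes in the primary FAS model. Only H5 has none. If H5 passed narrowly, no planned analysis on the responder scale would show whether the result depends on the exclusions.

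**Working it through.** **1. Is there a contradiction?** Reading Section 9.4.1, Section 9.5.1 and Table 4 together:

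| Hypothesis | Tier (9.4.1) | PP line | FAS line |
|---|---|---|---|
| H1, H2: OPA GMTs, 15 serotypes | primary | yes | yes |
| H3: ≥4-fold rise, 22F and 33F | primary | yes | yes |
| H4: serotype 3 OPA GMT | secondary | yes | no separate line; serotype 3 is in the primary FAS model |
| H5: serotype 3 ≥4-fold rise | secondary | yes | no |
| IgG GMCs; GMFRs and other ≥4-fold rises | secondary | yes | no |

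Every primary row has an FAS line and no secondary row has one. Text and table agree.

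**2. Who would an FAS analysis of H5 add?** Section 9.9.1 assumes a "90% evaluability rate (approximately 540 evaluable participants per treatment group". That checks: 600 × 0.90 = 540, leaving 60 per arm. The plan does not divide those 60 into missing samples and deviations. Without imputation, a participant lacking either titer enters neither analysis. Only deviation cases with both titers return, so 60 per arm is a ceiling.

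**3. How far could the bound move?** The documents give no serotype 3 response rates, so these are assumptions: 540 per arm in PP, comparator rates from 30% to 70%, an unstratified Miettinen and Nurminen 95% bound, and a PP result exactly at the pass mark.

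Smallest PP difference that passes H5:

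| Comparator rate | 30% | 35% | 40% | 50% | 60% | 70% |
|---|---|---|---|---|---|---|
| Difference (points) | 5.60 | 5.79 | 5.91 | 5.96 | 5.77 | 5.32 |

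The standard errors run from 2.71 to 3.03 points.

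Now restore *m* per arm at a 50% comparator rate (standard error 3.03). If those restored show no treatment difference, two things happen:

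- dilution of the estimate = 5.96 × m/(540 + m)
- gain from a narrower interval = 1.96 × 3.03 × (1 − √(540/(540 + m)))

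For m = 30, dilution is 5.96 × 30/570 = 0.31 and the gain is 5.94 × (1 − √(540/570)) = 0.16. The net change is about −0.15 points, or 0.15/3.03 = 0.05 standard errors.

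For m = 60, dilution is 0.60 and the gain 0.30, a net of about −0.29 points (0.10 standard errors).

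If those restored share the PP effect, there is no dilution and only the gain remains. For m = 30 the bound rises by about 0.16 points.

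| Restored per arm | No treatment difference | Same effect as PP |
|---|---|---|
| 5 | −0.03 | +0.03 |
| 10 | −0.05 | +0.05 |
| 20 | −0.10 | +0.11 |
| 30 | −0.15 | +0.16 |
| 60 (ceiling) | −0.29 | +0.31 |

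**4. When would PP and FAS disagree?** At 50%, with 30 restored and no difference among them, the FAS bound reaches 0 when the PP difference is 6.12 points (PP lower bound 0.16). The two sets disagree only for PP differences between 5.96 and 6.12 points.

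**5. Cross-treated participants.** They can be left out of PP, but the FAS counts them as randomised, so they would be expected to carry a reversed effect. With 5 per arm and fully swapped rates, the difference becomes 5.96 × (540 − 5)/545 = 5.85, a fall of 0.11. The narrower interval returns about 0.03, for a net of about −0.08 points. With 2 per arm the net is about −0.03.

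**The case for a change.** The strongest argument for adding the row is that it costs almost nothing: one further run of the H3 FAS program, one table line and one sentence, with no effect on alpha, sample size or power. Specifying it now would avoid a post hoc analysis if H5 came out borderline. H5 is indeed the only formal hypothesis without the check, and the FAS titer model does not answer the question on the ≥4-fold-rise scale.

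The bound can also be moved a good deal further under harsher assumptions. Take PP rates of 67% and 60%, which give a lower bound of +1.3 points. Add 60 per arm who respond at 30% on V114 and 60% on the comparator, and the bound becomes −2.2. With 45% on V114 it becomes −0.7; with 67% it rises to +1.6.

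The low cost and the uniqueness of the gap stand. The harsher cases carry less weight. They need all 60 non-evaluable participants per arm to have paired titers and a strongly reversed effect. The one source of reversal that the plan implies is cross-treatment, which shifts the bound by about 0.08 points at 5 per arm.

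**Conclusion.** No change follows. The missing row comes from one rule applied evenly: FAS analyses for primary endpoints, none for secondary ones. Sharing a method with H3 does not make H5 primary.

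An added row would gain little:

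- The H5 decision rests on PP and would stay there.
- PP membership is determined before final unblinding, and participants remain in their randomised group, so the set cannot be shaped to suit the result.
- Section 9.8 leaves H5 out of the rule for meeting the primary objectives.
- A PP lower bound within 0.16 points of zero already tells the reader that the result is marginal.
- The FAS titer model will show whether exclusions disturb the serotype 3 comparison on the GMT scale. H4 needs nothing further, since its FAS interval can be read against 1.2 directly.

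The size, with 30 restored per arm at a 50% comparator rate, is about −0.15 to +0.16 points, or 0.05 standard errors, with the sign unknown. This rests on assumed response rates and an assumed number restored; the plan supplies neither.

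A sponsor who wants the estimate can add it as a supportive analysis. Section 9 allows changes to non-confirmatory analyses to be recorded in a supplemental SAP before unblinding. That is a matter of preference and does not correct anything in the plan.

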9.5.2 Safety Analysis Populations

Safety analyses will be conducted in the All Participants as Treated (APaT) population, which consists of all randomized participants who received study vaccination. Participants will be included in the group corresponding to the study vaccination they actually received for the analysis of safety data using the APaT population. This will be the group to which they are randomized except for participants who take incorrect study vaccination; such participants will be included in the treatment group corresponding to the study vaccination actually received.

At least 1 temperature measurement obtained subsequent to study intervention is required for inclusion in the analyses of temperature.

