1.3 Schedule of Activities (SoA)

Study Period	Intervention				Notes
Visit Number	1	Telephone Contact	2	Telephone Contact	
Scheduled Time	Day 1	Day 15	Day 30	Month 6	
Visit Windows		Day 15 to Day 19 after Visit 1	Day 30 to Day 44 after Visit 1	Day 166 to Day 194 after Visit 1	
Administrative Procedures					
Screening Procedures					
Informed Consent	X				Consent must be obtained before any study procedures.
Informed Consent for Future Biomedical Research	X				Participation in future biomedical research is optional and consent must be obtained before the blood sample (DNA sample) is collected.
Assignment of Screening Number	X				
Inclusion/Exclusion Criteria	X				Review of prior medications/vaccinations, a complete physical examination, and temperature measurement are required at Visit 1 to determine eligibility.
Medical History	X				The participant's relevant medical history for the 5 years prior to study entry will be reviewed. History of tobacco use will also be collected for all participants.
Post-Randomization Procedures					
Assignment of Randomization Number	X				
Participant Identification Card	X				
Prior/Concomitant Medication and Non-Study Vaccination Review	X	X	X		
V114/Prevnar 13™ Administration (Blinded)	X				Participants will receive either a single dose of V114 or a single dose of Prevnar 13™.
Provide electronic Vaccination Report Card (eVRC)	X				Participants will be provided an eVRC to record adverse events (AEs) and body temperature measurements (see Section 8.3.4 for details).
Review eVRC Data With Participant		X	X		See Section 8.1.9 for details.
Collect eVRC From Participant			X		
Complete Telephone Contact Questionnaire				X	See Section 8.1.10 for details.

Study Period	Intervention				Notes
Visit Number	1	Telephone Contact	2	Telephone Contact	
Scheduled Time	Day 1	Day 15	Day 30	Month 6	
Visit Windows		Day 15 to Day 19 after Visit 1	Day 30 to Day 44 after Visit 1	Day 166 to Day 194 after Visit 1	
Safety Procedures					
Complete Physical Examination	X				To be performed by the investigator or medically qualified designee before vaccine is administered.
Pregnancy Test – if applicable	X				A pregnancy test consistent with local requirements (sensitive to at least 25 IU beta human chorionic gonadotropin [β -hCG]) must be performed before administration of study vaccine in females who are of reproductive potential (see Section 8.3.2 for details).

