8.1.9 Electronic Vaccination Report Card (eVRC)

The eVRC was developed to be administered electronically via a hand-held device. This item was structured as recommended in the final Food and Drug Administration Patient-Reported Outcome Guidance [U.S. Food and Drug Administration 2009]. The investigator or delegate will train the participant in the use of the eVRC at Visit 1 (Day 1).

Temperatures, injection-site reactions, vaccine-specific complaints, other complaints or illnesses, and concomitant medications or vaccinations will be recorded on the eVRC as

described in Section 1.3 and Section 8.3.4. The investigator or delegate will review the data captured on the eVRC with the participant at the Telephone Contact (Day 15) and Visit 2 (Day 30).

Any differences between eVRC data and the clinical database must be clearly explained in the participant's source documentation.

For the specific AEs collected via the eVRC, the investigator will use the information provided by the participant both on the eVRC and verbally at the time of eVRC review to apply the appropriate assessment of intensity and toxicity as described in Appendix 3.

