8.3.4 Safety Assessments and Use of the eVRC

All participants will be observed for at least 30 minutes after each vaccination for any immediate reactions. If any immediate AEs are observed during this period, the time at which the event occurred within this timeframe, as well as the event itself, any concomitant medications that were administered, and resolution of the event must be recorded on the appropriate eCRF.

Participants will use the eVRC (Section 8.1.9) to document the following information:

- Oral body temperatures measured Day 1 (day of vaccination) through Day 5 postvaccination
- Solicited injection-site AEs (redness/erythema, swelling, and tenderness/pain) Day 1 through Day 5 postvaccination
- Solicited systemic AEs (muscle pain/myalgia, joint pain/arthralgia, headache, and tiredness/fatigue) Day 1 through Day 14 postvaccination
- Any other injection-site or systemic AEs Day 1 through Day 14 postvaccination
- Concomitant medications and nonstudy vaccinations Day 1 to Day 14 postvaccination

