9.9.2 Sample Size and Power for Safety Analyses

The probability of observing at least 1 SAE in this study depends on the number of participants vaccinated and the underlying incidence of participants with an SAE in the study population. Calculations below assume that 100% of the randomized participants will be evaluable for safety analyses. There is an 80% chance of observing at least 1 SAE among 600 participants in V114 group if the underlying incidence of an SAE is 0.27% (1 of every 373 participants receiving the vaccine). There is a 50% chance of observing at least 1 SAE among 600 participants in the V114 group if the underlying incidence of an SAE is 0.12% (1 of every 866 participants receiving the vaccine). If no SAEs are observed among

600 participants, this study will provide 97.5% confidence that the underlying percentage of participants with an SAE is <0.61% (1 in every 163 participants) in the V114 group.

Table 6 summarizes the percentage point differences between the 2 vaccination groups that could be detected with 80% probability for a variety of hypothetical underlying incidences of an AE.

Table 6 Differences in Incidence of Adverse Event Rates Between the 2 Vaccination Groups That Can be Detected With an Approximately 80% Probability

Incidence of Adverse Event		Risk Difference
V114 (%)	Prevnar 13™ (%)	Percentage Points
1.6	0.1	1.5
5.0	2.0	3.0
9.1	5.0	4.1
15.4	10.0	5.4
21.2	15.0	6.2
26.8	20.0	6.8
37.6	30.0	7.6

The incidences presented here are hypothetical and do not represent actual adverse experiences in either group. The incidences assume a 2-sided 5% alpha level with 600 participants in each group. No multiplicity adjustments were made.
The calculations are based on an asymptotic method proposed by Farrington and Manning (1990) [Farrington, C. P. 1990].

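### Does the all-vaccinated safety denominator understate solicited adverse events by treating participants without follow-up as event-free?

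*Combined protocol and SAP*

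**What the plan says.** Section 9.5.2 defines the safety population, APaT, as the one "which consists of all randomized participants who received study vaccination". The same section adds a single data requirement: "At least 1 temperature measurement obtained subsequent to study intervention is required for inclusion in the analyses of temperature". Nothing comparable is written for solicited AEs.

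Section 8.3.4 has participants enter both kinds of data on the electronic vaccination report card (eVRC): "Oral body temperatures measured Day 1 (day of vaccination) through Day 5 postvaccination" and "Solicited injection-site AEs (redness/erythema, swelling, and tenderness/pain) Day 1 through Day 5 postvaccination". Solicited systemic AEs are entered on the same card through Day 14.

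Solicited AEs are primary safety endpoints (Sections 3 and 9.1). They are Tier 1 in Section 9.6.2, so p-values and 95% confidence intervals for the between-arm difference are provided. Table 4 gives a missing-data approach for each immunogenicity endpoint; Table 5, for safety, has no such column. Section 9.9.2 states: "Calculations below assume that 100% of the randomized participants will be evaluable for safety analyses".

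**The concern.** Temperature and solicited AEs sit on the same diary, yet a vaccinated participant who returns nothing leaves the temperature denominator and stays in the solicited-AE one. Elsewhere the plan ties analysis membership to having data: "The FAS population consists of all randomized participants who received at least 1 vaccination and have at least 1 serology result". Section 7.3 refers to prespecified data-handling guidelines, but the documents show no such rule for solicited AEs. This can look like an oversight.

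If it were one, the error would favour the vaccine. Reactogenicity percentages would be too low and, with equal non-reporting, the difference between arms would be pulled towards zero. Unequal non-reporting could create a difference or hide one. The plan also does not promise to show how many participants lacked follow-up, so a reader could not size the effect.

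**Working it through.** **Inputs.** From Section 9.9.2 and Table 6: 600 per arm, 2-sided alpha 0.05, power about 80%, 100% evaluable. The fraction without solicited-AE follow-up, f, is not in the documents; 1% (6 per arm) and 5% (30 per arm) are assumptions.

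**Reproducing Table 6.** Power = Φ[(d − 1.96·SE0)/SE1], where d = p1 − p2, SE0 = √[2·p̄(1−p̄)/n] and SE1 = √{[p1(1−p1) + p2(1−p2)]/n}. For 37.6% versus 30.0%: p̄ = 0.338, SE0 = 0.02731, SE1 = 0.02722, so (0.076 − 0.05353)/0.02722 = 0.826 and power is 79.5%. The seven rows give 80.9, 80.8, 79.3, 80.3, 79.7, 79.5 and 79.5%, in line with the stated 80%.

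**Equal non-reporting, unrelated to reactions.** The observed rate is p(1−f), so the difference is d(1−f).

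- f = 1%: 0.376 × 0.99 = 0.3722 and 0.300 × 0.99 = 0.2970, a difference of 7.52 points.
- f = 5%: 0.376 × 0.95 = 0.3572 and 0.300 × 0.95 = 0.2850, a difference of 7.22 points.

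**Cost of the rule itself.** Some power is lost whatever the rule, because the data are absent. The fair comparison sets scaled rates with n = 600 (all vaccinated) against unscaled rates with n = 594 or 570 (available data).

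| Rates | f | All vaccinated | Available data | Cost of rule (points) |
|---|---|---|---|---|
| 37.6 vs 30.0 | 1% | 78.9% | 79.1% | 0.2 |
| 37.6 vs 30.0 | 5% | 76.4% | 77.5% | 1.0 |
| 26.8 vs 20.0 | 1% | 79.0% | 79.1% | 0.1 |
| 26.8 vs 20.0 | 5% | 76.8% | 77.5% | 0.6 |
| 15.4 vs 10.0 | 1% | 79.8% | 79.9% | 0.1 |
| 15.4 vs 10.0 | 5% | 77.9% | 78.2% | 0.3 |

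The cost rises with incidence, so the top row of Table 6 is not a ceiling. At assumed rates of 58% versus 50% (79.5% power at f = 0), the same formula gives 78.6% against 79.1% at f = 1%, and 75.0% against 77.4% at f = 5%: costs of 0.5 and 2.4 points. The proportional shrinkage of the difference is still only f.

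**Unequal non-reporting (assumed 3% versus 1%, equal true rates).** The false difference is p × 0.02. At 30.0% it is 0.6 points and the 2-sided rejection rate is 5.6%. At 37.6% it is 0.75 points and 5.8%. No passage suggests a cause for such an imbalance: Section 6.3.3 keeps participants and follow-up staff blinded.

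**How likely is a sizeable f?** The Schedule of Activities lists "Review eVRC Data With Participant" at both the Day 15 telephone contact and Visit 2. Section 8.1.9 lets the investigator use verbal information given at those reviews, so an unused diary does not by itself mean no follow-up. Section 8.1.11 asks for Visit 2 activities at withdrawal, and Section 7.3 requires attempts to reach participants who miss a visit. A vaccinated participant contributes nothing only if all of these fail.

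**The case for a change.** The case for a change is that these are primary, tested endpoints, that the likely direction of error makes the vaccine look milder, and that a few sentences would settle the matter. A denominator limited to participants with an eVRC entry or a completed review, with the all-vaccinated version as a sensitivity analysis, would put solicited AEs on the same footing as temperature.

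The textual point stands: nothing visible says how a participant without solicited-AE follow-up is handled, and the event-free reading follows from the definition. The rest is weaker.

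- A maximum temperature or a titre has no value without a measurement, so a data requirement there is unavoidable. AEs are reports gathered through several routes, including the 30-minute observation of every participant. A requirement for one endpoint does not imply one for the other.
- A minimum of one eVRC entry removes only those who report nothing. Someone who stops on Day 2 would still be counted as event-free for systemic AEs through Day 14.
- If the 30-minute observation did not count as follow-up, a participant with pain seen in that window and no later contact would leave the main Tier 1 analysis, event included. APaT keeps that event.
- Restricting to available data relies on non-reporting being unrelated to reactions, which cannot be checked for those who report nothing.

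Section 9.6.3 already displays reasons for discontinuation and Section 9.12 the number vaccinated, so a reader has part of the information. The exact count of participants without solicited-AE follow-up is not promised; that is the one useful remnant.

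**Conclusion.** The plan states a reproducible and conventional denominator: participants with a reported event among those vaccinated. The event-free treatment is an inference from that definition, and no figure in the plan is wrong. At the only evaluability the documents give (100%), the effect is zero. At an assumed 5% equal non-reporting it takes 0.38 points off a 7.6-point difference (7.60 − 7.22) and, relative to available data, about 1 point off power in Table 6's top row; at the higher assumed rates it takes 2.4. The safety objective has no hypothesis or success criterion, and Section 9.6.2 bases the assessment on clinical review, so no trial conclusion depends on it.

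This rests on non-reporting being small and similar in the two arms, which dense follow-up and blinding make reasonable but which only the data can confirm. Analysts can show the number without solicited-AE follow-up by arm beside the results, with no amendment to the plan. Replacing APaT would exchange one modest assumption for another, with no clear gain.
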